## 8.0 SAFETY AND ADVERSE EVENTS

### 8.1 Definitions

#### ***Adverse Event***

An ***adverse event*** (AE) is any symptom, sign, illness or experience that develops or worsens in severity during the course of the study. Intercurrent illnesses or injuries should be regarded as adverse events. Abnormal results of diagnostic procedures are considered to be adverse events if the abnormality:

- results in study withdrawal
- is associated with a serious adverse event
- is associated with clinical signs or symptoms
- leads to additional treatment or to further diagnostic tests
- is considered by the investigator to be of clinical significance

#### ***Serious Adverse Event***

Adverse events are classified as serious or non-serious.

A ***serious adverse event*** is any AE that is:

- fatal
- life-threatening
- requires or prolongs hospital stay
- results in persistent or significant disability or incapacity
- a congenital anomaly or birth defect
- an important medical event

Important medical events are those that may not be immediately life threatening, but are clearly of major clinical significance. They may jeopardize the subject, and may require intervention to prevent one of the other serious outcomes noted above. For example, drug overdose or abuse, a seizure that did not result in in-patient hospitalization, or intensive treatment of bronchospasm in an emergency department would typically be considered serious.

All adverse events that do not meet any of the criteria for serious should be regarded as ***non-serious adverse events***.

#### ***Adverse Event Reporting Period***

The study period during which adverse events must be reported is normally defined as the period from the initiation of any study procedures to the end

of the study treatment follow-up. Adverse event reporting will continue until 90 days following their operation or the end of their index hospitalization (whichever is longer).

### ***Preexisting Condition***

Preexisting conditions that can worsen during the study period will only be reported if they are related to the study intervention.

### ***Post-study Adverse Event***

All unresolved adverse events should be followed by the investigator until the events are resolved, the subject is lost to follow-up, or the adverse event is otherwise explained. At the last scheduled visit, the investigator should instruct each subject to report any subsequent event(s) that the subject, or the subject's personal physician, believes might reasonably be related to the interventions in this study. The investigator should notify the IRB of any death or adverse event occurring at any time after a subject has discontinued or terminated study participation that may reasonably be related to the study interventions.

### ***Abnormal Laboratory Values***

A clinical laboratory abnormality related to the study interventions should be documented as an adverse event if any one of the following conditions is met:

- The laboratory abnormality is not otherwise refuted by a repeat test to confirm the abnormality
- The abnormality suggests a disease and/or organ toxicity
- The abnormality is of a degree that requires active management; e.g. change of dose, discontinuation of the drug, more frequent follow-up assessments, further diagnostic investigation, etc.

### ***Hospitalization, Prolonged Hospitalization or Surgery***

Any adverse event that results in hospitalization or prolonged hospitalization should be documented and reported as a serious adverse event unless specifically instructed otherwise in this protocol. Any condition responsible for surgery should be documented as an adverse event if the condition meets the criteria for and adverse event.

Neither the condition, hospitalization, prolonged hospitalization, nor surgery are reported as an adverse event in the following circumstances:

- Hospitalization or prolonged hospitalization for diagnostic or elective surgical procedures for a preexisting condition. Surgery should **not** be reported as an outcome of an adverse event if the purpose of the surgery was elective or diagnostic and the outcome was uneventful.

- Hospitalization or prolonged hospitalization required to allow efficacy measurement for the study.
- Hospitalization or prolonged hospitalization for therapy of the target disease of the study, unless it is a worsening or increase in frequency of hospital admissions as judged by the clinical investigator.

## **8.2 Recording of Adverse Events**

At each contact with the subject, the investigator must seek information on adverse events by specific questioning and, as appropriate, by examination. Information on all adverse events should be recorded immediately in the source document, and also in the appropriate adverse event module of the case report form (CRF). All clearly related signs, symptoms, and abnormal diagnostic procedures results should be recorded in the source document, though should be grouped under one diagnosis.

All adverse events occurring during the study period must be recorded if related to the study interventions.

The clinical course of each event should be followed until resolution, stabilization, or until it has been determined that the study treatment or participation is not the cause. Serious adverse events that are still ongoing at the end of the study period must be followed up to determine the final outcome. Any serious adverse event that occurs after the study period and is considered to be possibly related to the study interventions should be recorded and reported immediately.

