### **3.4 Primary Safety Endpoints**

*Perioperative complications, morbidity, mortality, and hospital readmission will all be tracked*

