### **8.5.1 Medical Monitoring and AE/SAE Reporting**

A Medical Monitor is assigned to this study at the Thomas Jefferson University. This is a physician/pharmacist who is not directly involved in the trial, and is not currently collaborating with the sponsor/investigator on any other trial. The role of the Medical Monitor is to review all reportable AEs/SAEs (in real-time) including grading, toxicity assignments, non-reportable AEs (quarterly), protocol violations/deviations, as well as

all other safety data and activity data observed in the ongoing clinical trial occurring at Thomas Jefferson University. The Medical Monitor may recommend reporting of adverse events and relevant safety data, and may also recommend suspension or termination of the study to the DSMC and TJU IRB.

Every KCC investigator initiated protocol includes requirements for reporting of adverse events based on CTC 4.0. All events are reported to the IRB and Medical Monitor using a password protected web-site. In addition all unexpected and serious adverse events (SAEs) are reported to the TJU IRB and to the Food and Drug Administration (FDA) if applicable. The investigator is required to submit all unexpected and serious adverse events to the TJU IRB and the Medical Monitor within the timeframes outlined in the below table. All AE/SAEs will be reported to the DSMC at the quarterly DSMC review meetings; however, if the Medical Monitor determines corrective action is necessary, an “ad hoc” DSMC meeting will be called. **Fatal adverse events related to treatment which are unexpected must be reported within 24 hours to the TJU IRB and the DSMC. Fatalities not related to the study drug/device must be reported within 5 days.** A summary of the reporting requirements for KCC investigator initiated Phase I and Phase II studies are presented below.

AE/SAE’s related to the study interventions are being tracked by the attending physicians caring for the patients in real time during their hospital stay and recorded on complication cards. This is also supplemented with chart review information. This data will be used to keep study intervention AE logs for each patient. After discharge, study subjects are continued to be tracked at the postoperative outpatient office visits up to 90 days post operation by the attending physicians.

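### Section 8.2 contradicts itself on whether all adverse events or those related to the interventions are recorded; a relatedness filter would make adverse-event data outside the named endpoints non-comparable between arms

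*Combined protocol and SAP*

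**What the plan says.** Section 8.2 contains two recording rules. The first has no relatedness condition and covers the case report form as well as the source document: "Information on all adverse events should be recorded immediately in the source document, and also in the appropriate adverse event module". The second, in the next paragraph, has one: "All adverse events occurring during the study period must be recorded if related to the study interventions".

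The rest of the safety text is divided in the same way.

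- **No relatedness condition.** Under 8.1 an adverse event "is any symptom, sign, illness or experience that develops or worsens in severity during the course of the study". The 8.1 rule on hospitalization makes events that cause or prolong a hospital stay serious adverse events, with listed exceptions that do not turn on relatedness.
- **Relatedness condition.** 8.1 on laboratory findings: "A clinical laboratory abnormality related to the study interventions should be documented as an adverse event if any one of the following conditions is met". 8.1 on pre-existing conditions: "Preexisting conditions that can worsen during the study period will only be reported if they are related to the study intervention". 8.5.1 introduces the complication cards, supplemented by chart review and feeding the event logs, by saying that events "related to the study interventions are being tracked by the attending physicians caring for the patients in real time".

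The endpoint sections carry no relatedness condition. Section 3.4 says: "Perioperative complications, morbidity, mortality, and hospital readmission will all be tracked". Section 3.3 lists readmission and the complications as secondary endpoints. Section 7.2 compares these between arms and makes readmission the primary safety outcome, with a two-arm Bayesian stopping rule.

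**The concern.** Section 5.1 assigns the package to the intervention arm, while controls follow the standard 7-day pathway. Sections 3.1 and 5.9 state that the trial is not blinded. Relatedness to the study interventions can therefore be judged meaningfully in one arm only, by staff who know the allocation. Used as a condition for recording, it removes control-arm events from the data before any analysis.

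The exposed data are the harms that are not named endpoints. Sections 1.6 and 5.3 single out falls during early mobilization and dehydration after discharge as risks of this research, and neither is in the 3.3 list. A fall or dizzy spell in a control patient would have no evident route into the record under the narrower rule, so the same event in the pathway arm would have no comparator.

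A second question concerns the endpoints themselves. The hypothesis requires no increase in perioperative complications. The instruments described for capturing complications are the cards, chart review and logs of 8.5.1, and these are introduced as tracking related events. The plan does not say whether they also supply the 3.3 and 3.4 endpoints for both arms.

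**Working it through.** The plan states no figure on this point, so there is nothing to reproduce. The check is a comparison of the text, followed by one illustration.

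**Step 1. Can the two 8.2 sentences be reconciled?** If every event is recorded in the source document and the case report form, the second sentence adds no event to the record. It has an effect only if it restricts recording, or if it marks a mandatory minimum (must) inside a broader expectation (should). The text does not say which. Staff recording everything and staff recording related events alone could both claim compliance.

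**Step 2. Does the rest of the plan settle it?**

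| Place | Relatedness condition? |
|---|---|
| 8.1 Adverse event definition | No |
| 8.1 Hospitalization rule | No |
| 8.2, first rule | No |
| 8.2, second rule | Yes |
| 8.1 Preexisting condition | Yes |
| 8.1 Abnormal laboratory values | Yes |
| 8.5.1 Complication cards and logs | Yes |
| 3.3, 3.4 and 7.2 endpoints | No |

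It does not. The DSMC text in 8.5.1 is split as well: one paragraph sends all adverse events to the quarterly review, and a later one withholds the common postoperative complications as unrelated to the interventions.

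**Step 3. Which data are exposed?** Readmission, mortality, overall complications and the named complications are defined without the condition, and all but mortality have a stated between-arm analysis in 7.2. What remains exposed is the general adverse-event record, including falls, dehydration and laboratory abnormalities.

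**Step 4. Illustration for the adverse-event record only.** Inputs:

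- n = 71 per arm, from 7.1.
- Assumption: no control event is judged related, so controls have 0 of 71 recorded.
- Assumption: true event rates are equal, at 50% of patients in each arm. The 50% is a round value suggested by the figure for pancreaticoduodenectomy patients in 8.5.1. It is not an estimate for this trial's selected population.
- Assumption: a share q of pathway-arm events is judged related, varied from 5% to 30%.

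For 5 versus 0 of 71, the two-sided Fisher p is 2 × C(71,5)/C(142,5) = 0.058. For 6 versus 0 it is 2 × C(71,6)/C(142,6) = 0.028. Six recorded events are therefore enough for p < 0.05. With r = 0.5 × q, the probability of that result is P(X ≥ 6) for X ~ Binomial(71, r).

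| q | r | Expected records, 71 × r | P(p < 0.05) |
|---|---|---|---|
| 5% | 2.5% | 1.8 | 0.9% |
| 10% | 5% | 3.6 | 14% |
| 20% | 10% | 7.1 | 73% |
| 30% | 15% | 10.7 | 97% |

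Only the product r matters, so another base rate with a matching q gives the same row. With the 69 per arm of the Study Summary, the threshold is again six events (p = 0.028). The true rates are equal throughout, so every such result would be an artefact of recording.

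**The case against.** The strongest reply is that the harms on which the trial's claim rests do not depend on the 8.2 sentence. The Study Summary schema collects complications prospectively after randomization to either pathway, 3.4 tracks complications, morbidity, mortality and readmission, and 7.2 compares readmission and complications between arms. A reader might infer that harms cannot be compared at all. The documents do not support that, because nothing says that endpoint data come from the related-event log alone.

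Four further objections have weight.

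- The disputed sentence does not contain the word only. A filter is one reading of it, and another sentence in the same section requires all events.
- A reader might apply the complication rate of more than 50% in 8.5.1 to the sample size and count the patients whose events would be lost. That rate describes pancreaticoduodenectomy patients in general and appears in a paragraph about DSMC submission. Sections 4.1 and 4.2 select patients with a firm gland and exclude several comorbidities and operative difficulties. No such count can be derived.
- A reader might infer that the filter favours the pathway. Too few recorded control events would make the pathway look worse, so this mechanism could not falsely support a claim of no increase.
- The contrast between arms is not absolute: item 5a of 5.1 is worded as volume restriction for all patients, and item 6 applies to both groups. The plan also does not name the attending surgeons as judges of relatedness, and 8.5.1 provides a Medical Monitor not directly involved in the trial who reviews grading and toxicity assignments.

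These points limit the concern but do not remove it. The Medical Monitor can review only what has been recorded. Defining an endpoint without a relatedness condition does not say how it is captured, and the plan does not clearly name an instrument that captures unrelated complications equally in both arms.

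**Conclusion.** The concern holds as an internal contradiction with a limited but real consequence. The plan does not settle whether all adverse events or related ones are recorded. Under the narrower reading, adverse-event data outside the prespecified endpoints would not be comparable between arms, and the capture of the 3.3 and 3.4 complication endpoints is left unclear. The primary endpoint, the readmission stopping rule and the definitions of the complication endpoints are not affected.

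The size cannot be fixed from the documents. The illustration runs from negligible (0.9%) to near certain (97%) for a spurious difference in the adverse-event record, depending on how many pathway-arm events are judged related. It rests on no control event being judged related and on the narrower rule being followed. It says nothing about readmission or the named complications. The wording should be corrected because the choice determines what is collected, and events left unrecorded may not be recoverable later.

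**What to change.** 1. Replace the second rule in 8.2 with a single rule: all adverse events and complications are recorded in both arms, with the same definitions and the same instrument, through the window already set in 8.1 (90 days after operation, or the end of the index hospitalization if longer). Relatedness is a separate field and not a condition for recording.
2. Align the 8.1 paragraphs on laboratory values and pre-existing conditions with that rule.
3. State in 8.5.1 that the complication cards plus chart review cover all complications in both arms, and that they are the source for the 3.3 and 3.4 endpoints.
4. Reconcile the two statements in 8.5.1 on which events are reported to the DSMC.

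The cost is protocol wording and somewhat more data entry. Attending physicians already track patients in hospital and at outpatient visits to 90 days, and chart review is already planned. Sample size and the primary analysis do not change.

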## **8.4 Stopping Rules**

Stopping rules for efficacy and safety are outlined in the statistical analysis plan.

## **8.5 Data and Safety Monitoring Plan**

It is the responsibility of the Principal Investigator to oversee the safety of the study at his/her site. This safety monitoring will include careful assessment and appropriate reporting of adverse events as noted above, as well as the compliance and implementation of the KCC data and safety-monitoring plan. Medical monitoring will include a regular assessment of the number and type of serious adverse events by both the assigned Medical Monitor and the KCC DSMC.

### **8.5.1 Medical Monitoring and AE/SAE Reporting**

A Medical Monitor is assigned to this study at the Thomas Jefferson University. This is a physician/pharmacist who is not directly involved in the trial, and is not currently collaborating with the sponsor/investigator on any other trial. The role of the Medical Monitor is to review all reportable AEs/SAEs (in real-time) including grading, toxicity assignments, non-reportable AEs (quarterly), protocol violations/deviations, as well as

all other safety data and activity data observed in the ongoing clinical trial occurring at Thomas Jefferson University. The Medical Monitor may recommend reporting of adverse events and relevant safety data, and may also recommend suspension or termination of the study to the DSMC and TJU IRB.

Every KCC investigator initiated protocol includes requirements for reporting of adverse events based on CTC 4.0. All events are reported to the IRB and Medical Monitor using a password protected web-site. In addition all unexpected and serious adverse events (SAEs) are reported to the TJU IRB and to the Food and Drug Administration (FDA) if applicable. The investigator is required to submit all unexpected and serious adverse events to the TJU IRB and the Medical Monitor within the timeframes outlined in the below table. All AE/SAEs will be reported to the DSMC at the quarterly DSMC review meetings; however, if the Medical Monitor determines corrective action is necessary, an “ad hoc” DSMC meeting will be called. **Fatal adverse events related to treatment which are unexpected must be reported within 24 hours to the TJU IRB and the DSMC. Fatalities not related to the study drug/device must be reported within 5 days.** A summary of the reporting requirements for KCC investigator initiated Phase I and Phase II studies are presented below.

AE/SAE’s related to the study interventions are being tracked by the attending physicians caring for the patients in real time during their hospital stay and recorded on complication cards. This is also supplemented with chart review information. This data will be used to keep study intervention AE logs for each patient. After discharge, study subjects are continued to be tracked at the postoperative outpatient office visits up to 90 days post operation by the attending physicians.

We propose to submit to the DSMC for review all AE/SAE’s specifically related to the WARP protocol interventions. These include, renal injury related to the volume restriction, injury related to enhanced physical therapy such as a fall, intolerance of the intervention (full liquid) diet with dizziness or lightheadedness. Given the fact that more than 50% of all pancreaticoduodenectomy patients develop some postoperative complication, such as pancreatic fistula, delayed gastric emptying, intraabdominal abscess, wound infection, urine infection, heart attacks, arrhythmias, pulmonary complications, renal, strokes, and deep vein thrombosis, and that these bear no relation to the specific interventions of the WARP protocol, they will not be reported to the DSMC.

	Grade 1	Grade 2	Grade 2	Grade 3		Grade 3		Grades 4 and 5
	Unexpected and Expected	Unexpected	Expected	Unexpected with Hospitalization	Unexpected without Hospitalization	Expected with Hospitalization	Expected without Hospitalization	Unexpected and Expected
Unrelated Unlikely	Reviewed at	Reviewed at	Reviewed at	5 Working Days	Reviewed at Quarterly	5 Working Days	Reviewed at Quarterly	Phase 1 - 48 Hours

	Quarterly DSMC Meeting and IRB Annual Review	Quarterly DSMC Meeting and IRB Annual Review	Quarterly DSMC Meeting and IRB Annual Review		DSMC Meeting and IRB Annual Review		DSMC Meeting and IRB Annual Review	(Death: 24 Hours)  Phase 2 - 5 Working Days
Possible Probable Definite	Reviewed at Quarterly DSMC Meeting and IRB Annual Review	5 working days	Reviewed at Quarterly DSMC Meeting and IRB Annual Review	48 Hours (Death: 24 Hours)	Phase 1 - 48 Hours  Phase 2 - 5 Working Days	48 Hours (Death: 24 Hours)	Reviewed at Quarterly DSMC Meeting and IRB Annual Review	Phase 1 and Phase 2 - 48 Hours (Death: 24 Hours)

**\*\*NOTE:** This table is based on the NCI AE/SAE reporting Guidelines and the TJU IRB Policy and Procedures. Please follow the individual protocol AE/SAE reporting guidelines if more stringent reporting procedures are specified.

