### 1.2 Background and Rationale

Standardization of post-operative care pathways has resulted in improved perioperative outcomes following complex abdominal operations. This has resulted in a shorter length of stay for many patients.

In pancreaticoduodenectomy specifically, the implementation of a post-operative pathway here at Jefferson has reduced the median length of stay to seven days and demonstrated that a fair proportion of patients (10%) leave the hospital in as early as five days. There are many reasons to encourage a shorter length of stay for these complex patients including: potential benefit to early mobilization and return to the home setting, decrease in hospital-acquired infectious complications, and of increasing importance in the modern setting, potential cost savings.

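### Section 8.5.1 declares common post-pancreaticoduodenectomy complications unrelated in advance and keeps them from the DSMC; this conflicts with the DSMC reporting rules in 8.5 and 8.5.1, and no passage gives the DSMC complication counts by arm

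*Combined protocol and SAP*

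**What the plan says.** Section 8.5 provides for "a regular assessment of the number and type of serious adverse events by both the assigned Medical Monitor and the KCC DSMC". It sets no filter for relatedness. Section 8.5.1 adds: "All AE/SAEs will be reported to the DSMC at the quarterly DSMC review meetings".

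Later in 8.5.1, a trial-specific paragraph proposes to send the DSMC only events specifically related to the WARP interventions. One of its examples is "renal injury related to the volume restriction". It then reasons that "more than 50% of all pancreaticoduodenectomy patients develop some postoperative complication". It lists fistula, delayed gastric emptying, abscess, wound and urine infection, cardiac events, pulmonary and renal complications, stroke and deep vein thrombosis, and concludes that "these bear no relation to the specific interventions of the WARP protocol, they will not be reported to the DSMC".

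Elsewhere, section 2.1 makes the absence of an increase in complications part of the primary objective. Section 3.4 tracks complications under the primary safety endpoints, and section 7.2 compares them between arms as secondary outcomes.

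**The concern.** Two problems sit in the one paragraph.

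The first is a conflict of instructions. Staff following the general rule would send the listed events to the DSMC, and staff following the trial-specific paragraph would not.

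The second is that relatedness is settled in advance for outcomes the trial sets out to compare. Sections 1.6 and 5.3 name, as the major risk of the research, complications that arise after discharge and may be recognised late. If an earlier discharge pathway raises the frequency or severity of common complications, no single case will look attributable to the pathway. The signal is an imbalance between arms. A committee that receives only events already judged related cannot see that imbalance from those events.

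**Working it through.** **1. The reporting rules side by side**

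| Place | What reaches the DSMC | Relatedness filter |
|---|---|---|
| 8.5 | Number and type of SAEs | None |
| 8.5.1, general text | All AEs and SAEs, quarterly | None |
| 8.5.1, WARP paragraph | Only events related to the interventions; listed complications excluded | Set in advance, by event type |

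The first two rows agree with each other and the third does not. No sentence says which prevails.

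**2. Overlap with the trial's own endpoints**

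Section 3.3 names 7 complications. Four are on the excluded list directly: delayed gastric emptying, intra-abdominal abscess, wound infection and urinary infection. Three are there by near-equivalent terms: anastomotic leak (fistula), respiratory compromise (pulmonary) and renal failure (renal). So 4 + 3 = 7 of 7. The list also holds heart attack, arrhythmia, stroke and deep vein thrombosis, which 3.3 does not name.

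**3. Is the advance declaration consistent with the rest of the protocol?**

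- Section 1.2 gives "decrease in hospital-acquired infectious complications" as a reason for a shorter stay, and section 1.6 says that overall complications may fall. Wound and urine infection are nevertheless declared unrelated. An outcome that the pathway is expected to change in one direction cannot be unrelated by definition.
- Renal injury attributed to volume restriction is reportable, while renal complications in general are excluded. No written criterion separates the two.

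**4. Does the readmission rule fill the gap?**

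Inputs from section 7.2 (Safety): priors Beta(0.2, 0.8) for the 5-day arm and Beta(15, 85) for control, 36 patients per arm, and a stop if Pr(π_5day − π_control > 0.05) > 0.9. With x5 and xc readmissions, the posteriors are Beta(0.2 + x5, 36.8 − x5) and Beta(15 + xc, 121 − xc). Simulation from these reproduces the plan's table exactly: stop at 10, 11, 12 and 13 or more readmissions in the 5-day arm for 1–2, 3–5, 6–8 and 9–12 in control.

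- The rule depends on readmissions alone. If complications rose but readmission stayed at the protocol's 15% in both arms (an assumption), it would stop the trial at that look about 1.1% of the time.
- It starts at 72 patients: 72/142 = 50.7% of the section 7.1 total, or 72/138 = 52.2% of the Study Summary total.
- The section does not say who receives the result.

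**5. What a table by arm could show**

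At the protocol's figure of at least 50%, 0.50 × 36 = 18 or more patients per arm would have a complication at that look. Case-by-case attribution is a poor tool at that frequency. A comparison by arm is the right one but has limited sensitivity. The power of a two-sided 5% test is Φ{[d − 1.96√(2p̄(1 − p̄)/n)] / √[(p1(1 − p1) + p2(1 − p2))/n]}. With n = 36, p1 = 0.50 and an assumed p2 = 0.70, this is Φ{(0.20 − 0.226)/0.113} = 0.41. With p2 = 0.60 it is 0.13. The table would inform judgement and would not serve as a test.

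**The case against.** **A deliberate exception.** The general text in 8.5.1 is institutional wording that speaks of study drugs and devices. The WARP paragraph follows it, is specific to this trial and gives a reason. Reading it as an intended exception is natural. That stands as an account of intent, but the text does not say so. If it is an exception, its effect is to withhold the events.

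**Other safeguards.** These are real. All events go to the IRB and to a Medical Monitor who is not directly involved in the trial. The Monitor reviews toxicity assignments and all other safety data, and may recommend reporting, suspension or termination. If the Monitor finds corrective action necessary, an ad hoc DSMC meeting is called. Under section 8.5.2 the DSMC also receives the investigator's narrative, a summary report, the Monitor's recommendations and a review of outcome results. Its printout covers reported events, which could be read to include those reported to the Monitor. None of these is stated to be presented by arm.

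**Endpoint analysis is unaffected.** This is correct. Complications are still collected and compared under section 7.2. That section does not route the comparison to the DSMC while the trial is running.

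**Stronger readings that the documents do not support.** A reader might infer that these complications go unmonitored, or that the DSMC will never see them by arm. The safeguards above contradict the first. The institutional plan cited in section 8.5, which is not among the documents, leaves the second open. A reader might also infer that the reporting table overrules the exception, because its note says: "Please follow the individual protocol AE/SAE reporting guidelines if more stringent reporting procedures are specified". But the table is introduced with "A summary of the reporting requirements for KCC investigator initiated Phase I and Phase II studies are presented below", and the Study Summary gives this trial's phase as not applicable. The point does not rest on the table.

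**Conclusion.** The conflict between section 8.5, the general rule in 8.5.1 and the WARP paragraph is plain on the text and should be resolved. Declaring the listed complications unrelated in advance is not justified. They are part of the primary objective, tracked as safety endpoints, tied to the stated major risk, and expected by the protocol itself to respond to the pathway.

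The extent is all 7 complications named in section 3.3, plus cardiac events, stroke and deep vein thrombosis. It is not a count of missed harms, and the documents give no basis for estimating one. The conclusion about counts by arm is limited to these documents and could change if the institutional plan supplies them. The textual conflict would remain in any case. The recording wording in section 8.2 and the time limits for reporting fatalities are separate points.

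**What to change.** Delete the statement that the listed complications are unrelated and will not be reported to the DSMC, and reconcile sections 8.5 and 8.5.1 so that one rule applies. The common complications may be exempted from single-case DSMC reporting. In exchange, the DSMC should receive, at its existing quarterly meetings, a table by randomised arm of the number of patients with each section 3.3 complication, cardiac events, stroke, deep vein thrombosis, death and readmission, whatever relatedness was assigned. It should be built from the data already tracked under section 3.4 and analysed under section 7.2.

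The study statistician or data staff can prepare it. The aggregate table should go to the DSMC and not to the treating surgeons. In this unblinded trial they already know each patient's arm and course, but discharge by POD 5 is the primary endpoint and sections 1.3 and 5.1 leave discharge to their discretion.

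The cost is a wording amendment and at most 3 × 4 = 12 tables. The downside is slightly more DSMC paperwork and repeated looks without a formal boundary. With 7 complications, 4 further events (counting heart attack and arrhythmia separately), death and readmission, the table has 13 rows, and 13 × 12 = 156 possible comparisons. It should therefore be labelled descriptive and carry no p-values. No new stopping boundary is proposed.
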